4.4.4 Management of Temozolomide Related Adverse Events

The most common adverse reactions ($\geq 10\%$ incidence) are: alopecia, fatigue, nausea, vomiting, headache, constipation, anorexia, convulsions, rash, hemiparesis, diarrhea, asthenia, fever, dizziness, coordination abnormal, viral infection, amnesia, and insomnia.

The most common Grade 3 to 4 hematologic laboratory abnormalities ($\geq 10\%$ incidence) that have developed during treatment with temozolomide are: lymphopenia, thrombocytopenia, neutropenia, and leukopenia.

Allergic reactions have also been reported.

Please refer to [Appendix A](#) for dose modification algorithms for potential combination treatment related adverse events.

Table 0-8: Temozolomide Dosing Interruption or Discontinuation during Treatment Period

Toxicity	Temozolomide Interruption	Temozolomide Discontinuation	Reduce Temozolomide by 1 Dose Level
Absolute Neutrophil Count (ANC)	≥ 0.5 and $< 1.5 \times 10^9/L$	$< 0.5 \times 10^9/L$	≥ 0.5 and $< 1.0 \times 10^9/L$
Platelet Count	≥ 10 and $< 100 \times 10^9/L$	$< 10 \times 10^9/L$	≥ 10 and $< 50 \times 10^9/L$
NCI-CTCAE non-hematological toxicity (except for alopecia, nausea and vomiting)	Grade 2	Grade 3 or 4	Grade 3

Treatment with temozolomide may be continued when all of the following conditions are met:

- $ANC \geq 1.5 \times 10^9/L$
- Platelet count $\geq 100 \times 10^9/L$
- NCI-CTCAE non-hematological toxicity \leq Grade 1 (except for alopecia, nausea and vomiting)

Table 0-9: Temozolomide Dose Levels

Dose 0 (Assigned Starting Dose)	Dose Level 1	Dose Level 0	Dose Level -1
150 mg/m ² /day	200 mg/m ² /day	150 mg/m ² /day	100 mg/m ² /day

Please see [Appendix B](#) for Daily Dose Calculations by Body Surface Area (BSA).

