40. Schiff, D., et al., Phase 1 dose escalation trial of the safety and pharmacokinetics of cabozantinib concurrent with temozolomide and radiotherapy or temozolomide after radiotherapy in newly diagnosed patients with high-grade gliomas. *Cancer*, 2016. 122(4): p. 582-7.
doi:10.1097/CAD.000000000000108

APPENDIX A - DOSE MODIFICATION ALGORITHMS FOR POTENTIAL COMBINATION TREATMENT RELATED ADVERSE EVENTS

AE Terms & Descriptions	Dose Modification Algorithms
Diarrhea	
a. Grade 1-2 (duration < 48 hr)	a. Continue Cabozantinib at the current dose. If it does not improve with supportive measures consider a dose reduction. Continue temozolomide at the current dose.
b. Intolerable Grade 2 or Grade 3	b. Interrupt Cabozantinib and temozolomide until Grade ≤ 1 then consider restarting Cabozantinib at reduced dose. Dose reduce temozolomide by one dose level for Grade 3 only. Discontinue temozolomide for grade 4.
	c. Refer to the Table 0-3 for the management of diarrhea.
Neutropenia	
a. Neutrophil count <1.5	a. Interrupt temozolomide and cabozantinib until neutrophil count $\geq 1.5 \times 10^9/L$.
b. Neutrophil count <1.0	b. Interrupt temozolomide and cabozantinib until $\geq 1.5 \times 10^9/L$. Reduce temozolomide by 1 dose level. Continue cabozantinib at the same.
c. Neutrophil count <0.5	c. Discontinue temozolomide, interrupt cabozantinib until neutrophil count is $\geq 1.5 \times 10^9/L$ then resume at same dose.
Febrile Neutropenia	
Grade 3 or 4	Interrupt temozolomide and cabozantinib until resolved. Upon resumption, reduce temozolomide by 1 dose level. Continue cabozantinib at the same dose.
Thrombocytopenia	
Grade 1 or 2	Interrupt temozolomide until $\geq 100 \times 10^9/L$. Continue cabozantinib.

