Grade 2	
 • Cabozantinib treatment may be continued if PPES is tolerated. • Cabozantinib should be dose reduced or interrupted if PPES is intolerable. • Continue urea 20% cream twice daily AND high potency steroid cream (e.g., clobetasol 0.05%) once daily and add analgesics (e.g., NSAIDs/gamma-aminobutyric acid agonists) for pain control if needed. 
Reassess at least weekly; if PPES worsens or affects self-care, proceed to the intervention guidelines for Grade 3.
 
 • Continue temozolomide at the investigator's discretion
Grade 3	
 • Interrupt cabozantinib treatment until severity decreases to Grade 1 or 0. • Continue treatment of skin reaction with high potency steroid cream (e.g., clobetasol 0.05%) twice daily AND analgesics. • Resume study drug at a reduced dose if PPES recovers to Grade ≤ 1. • Discontinue subject from study treatment if PPES does not improve within 6 weeks • Interrupt/continue temozolomide at the investigator's discretion
Proteinuria (UPCR)	
≤ 1 mg/mg (≤ 113.1 mg/mmol)	
 • No change in cabozantinib or temozolomide treatment
> 1 and < 3.5 mg/mg (> 113.1 and < 395.9 mg/mmol)	
 • Refer to Table 0-6 for the management of cabozantinib treatment. No change in temozolomide treatment
≥ 3.5 mg/mg (≥ 395.9 mg/mmol)	
 • Refer to Table 0-6 for the management of cabozantinib treatment. No change in temozolomide treatment.
Nephrotic syndrome	
 • Discontinue cabozantinib
Hepatocellular Toxicity	
Grade 2 AST or ALT or Total Bili lasting longer than a week	
 • Interrupt cabozantinib and temozolomide until Grade 1. • Refer to the Section 4.4.3.13 for the management of DILI
Other Treatment Related Adverse Events (such as fatigue, nausea, vomiting, anorexia, weight loss, etc)	

Grade 1 or Grade 2 (tolerable)	
 • Add supportive care as indicated. • Continue cabozantinib and temozolomide treatment at the current dose; monitor as clinically indicated

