Intolerable Grade 2 or Grade 3	
 • Interrupt cabozantinib and temozolomide treatment until it is a Grade 1 or tolerable grade 2. Restart both cabozantinib and temozolomide at the current dose or dose reduced by one level.^b For Grade 3 AEs related to Temozolomide dose reduce by one level. • *Note: It is recommended that dose holds be as brief as possible
Grade 4-related to temozolomide Grade 4-related to cabozantinib (except clinically non-relevant laboratory abnormalities)	
 • Discontinue temozolomide. • Subjects should have cabozantinib interrupted immediately. • Discontinue cabozantinib unless the following criteria are met: Subject is deriving clear clinical benefit as determined by the investigator Toxicity can be managed with a dose reduction following recovery to Grade 1 (or baseline) and optimal medical care
Study treatment dose adjustment is only needed if the toxicity was deemed related to cabozantinib treatment or had an unclear relationship to cabozantinib treatment. ^b except nausea, vomiting, and alopecia- no dose interruption required for temozolomide	

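### Temozolomide dose rules conflict: Table 0-8 both stops and reduces at Grade 3, Appendix A is looser at Grade 2 with no order of precedence, and infection is left unresolved

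*Combined protocol and SAP*

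**What the plan says.** Two places tell a site what to do with temozolomide when a non-hematological event occurs.

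- **Section 4.4.4, Table 0-8.** The row "NCI-CTCAE non-hematological toxicity (except for alopecia, nausea and vomiting") puts Grade 2 under interruption, Grade 3 or 4 under discontinuation, and Grade 3 again under reduction by one level. Below the table, "Treatment with temozolomide may be continued when all of the following conditions are met"; one of those conditions is toxicity of Grade 1 or less, with the same three exceptions. Tolerability is not mentioned.
- **Appendix A, residual row.** Its heading is "Other Treatment Related Adverse Events (such as fatigue, nausea, vomiting, anorexia, weight loss, etc"). For Grade 1 or tolerable Grade 2 the action is "Continue cabozantinib and temozolomide treatment at the current dose; monitor as clinically indicated". For intolerable Grade 2 or Grade 3 it is "Interrupt cabozantinib and temozolomide treatment until it is a Grade 1 or tolerable grade 2", and then "For Grade 3 AEs related to Temozolomide dose reduce by one level". Temozolomide stops at a related Grade 4 event.
- **Appendix A, diarrhea row.** "Dose reduce temozolomide by one dose level for Grade 3 only. Discontinue temozolomide for grade 4".

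Sections 4.4 and 4.4.4 both send the reader to Appendix A, and 4.4.4 then prints Table 0-8 with its own conditions. No sentence ranks the two. Infection has a section of its own, 4.4.3.14, which holds cabozantinib until healing is complete and does not mention temozolomide. Appendix A has a febrile neutropenia row but no infection row.

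**The concern.** Two sites can handle the same event in opposite ways and both be following the protocol. At Grade 3, one cell of Table 0-8 ends temozolomide and the next keeps the subject on it at a lower dose. Section 4.8 makes the specific conditions of section 4.4 grounds for stopping study treatment, so the discontinuation cell cannot be dismissed as advice. At tolerable Grade 2, one rule withholds an alkylating agent and the other gives it.

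Infection is where this bears most on safety. Section 8.2.2 warns of myelosuppression and Pneumocystis pneumonia with temozolomide. A related infection outside febrile neutropenia reaches Appendix A only through the open end of the residual row's list, where the instruction at tolerable Grade 2 is to continue. What is at stake is subject safety, uniform dosing, and a clear standard for judging protocol deviations.

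**Working it through.** **Rules side by side (temozolomide, treatment-related events)**

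| Situation | Table 0-8 | Appendix A |
|---|---|---|
| Tolerable Grade 2 fatigue, anorexia, weight loss | Hold until Grade 1 or less | Continue |
| Grade 2 diarrhea under 48 h | Hold | Continue |
| PPES, Grade 2 | Hold | Investigator's choice |
| PPES, Grade 3 | Discontinue, and also reduce | Investigator's choice |
| Grade 2 liver tests | Hold | Hold only if longer than a week |
| Grade 3, diarrhea or residual row | Discontinue, and also reduce | Reduce |
| Grade 4, diarrhea or residual row | Discontinue | Discontinue |
| Tolerable Grade 2 infection outside febrile neutropenia | Hold | No row; residual row by default, so continue |
| Nausea, vomiting, alopecia | Excepted | Excepted (footnote b) |

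Three things follow.

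1. Table 0-8 keeps discontinuation and reduction apart in its other rows: ANC below 0.5 against 0.5 to below 1.0, and platelets below 10 against 10 to below 50 (×10⁹/L). Only the non-hematological row overlaps, at Grade 3. With Appendix A's reduce-then-discontinue pattern, this points to an error in one cell.
2. For neutropenia the two places agree. Appendix A's row ("Interrupt temozolomide and cabozantinib until neutrophil count" recovers) uses the same cut-offs of 1.5, 1.0 and 0.5. The disagreement lies in the non-hematological rows, and it covers several of them.
3. Footnote b of Appendix A exempts only nausea, vomiting and alopecia, so it does not reconcile the rest.

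**Size for one subject**

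Inputs: 150 mg/m² on Days 1-5 of Cycle 1 and 200 mg/m² from Cycle 2 (section 4.3); 28-day cycles, with Cycle 4 Day 1 at week 12; dose level -1 is 100 mg/m² (Table 0-9); missed doses are skipped (section 5.0, footnote j).

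Planned dose before Cycle 4 Day 1: 5 × 150 + 2 × 5 × 200 = 750 + 2000 = 2750 mg/m².

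*Grade 2 infection lasting through Cycle 2 Days 1-5.* Table 0-8 gives 0. The residual row gives either:
- 5 × 150 = 750 mg/m², which is 750/2750 = 27%, if continuing at the current dose is read as blocking escalation; or
- 5 × 200 = 1000 mg/m², which is 1000/2750 = 36%, if the dose is escalated as section 4.2 directs when ANC is at least 1.5 and platelets at least 100 (×10⁹/L).

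A shorter overlap costs less. At 150 mg/m², one day is 150/2750 = 5.5% and three days are 450/2750 = 16%. An infection that clears between courses costs nothing.

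*Grade 3 event in Cycle 1, resolved by Cycle 2 Day 1.* Discontinued: 0 in Cycles 2-3. Reduced from 150 to 100 mg/m² and kept there: 2 × 5 × 100 = 1000 mg/m². The gap is 1000/2750 = 36%.

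**The case against.** The best reply is that Appendix A is the operative document. It is headed for the combination, sections 4.4 and 4.4.4 both point to it, and it is looser than Table 0-8 in several non-hematological rows, which looks deliberate. On that view Table 0-8 is the single-agent rule and gives way. This has weight. It means the residual row is not a lone outlier, and a blanket rule that Table 0-8 prevails would overturn an explicit choice for fatigue, anorexia and weight loss. But the reading is nowhere stated, 4.4.4 prints Table 0-8 as live instruction straight after the reference, and no order of precedence cures a Table 0-8 row that contradicts itself.

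A reader might also infer that the plan lets cabozantinib be given before an infection has healed. The documents do not support that. Section 4.4.3.14 is explicit, the note under Table 0-2 sends the reader to section 4.4.3 for cabozantinib, and section 4.4 allows interruption for cabozantinib-related events at any time. Only the temozolomide question is open.

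The percentages are illustrations. They need the infection to span all five dosing days, and they need footnote j, written around scheduling, to apply to toxicity holds. Infection reaches the residual row only if judged treatment-related. Tolerability is itself a site judgement, so some variation is built in. All of this stands.

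**Conclusion.** The temozolomide rules are wrong as written at Grade 3, where Table 0-8 gives two incompatible actions. At Grade 2 they conflict without a ranking: Table 0-8 holds, and Appendix A's residual, diarrhea, PPES and hepatocellular rows are looser. For a related infection outside febrile neutropenia, whether to hold temozolomide is unresolved.

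The consequence for one subject ranges from nothing to 27% or 36% of the temozolomide planned before week 12 in the Grade 2 case, and is 36% in the Grade 3 case if 100 mg/m² is kept. The documents give no frequency for either case. Section 4.4.4 lists viral infection among reactions seen in at least 10% of temozolomide subjects, but that covers any grade and is not a rate for this case.

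A reader might infer that uneven dosing distorts the week-12 rate or the Simon decision rule. The documents give no basis for that, and it is not claimed. The point concerns safety and consistent conduct.

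**What to change.** 1. In Table 0-8, change the non-hematological discontinuation cell from Grade 3 or 4 to Grade 4 and keep one-level reduction at Grade 3, matching Appendix A.
2. State in section 4.4.4 and at the head of Appendix A that Appendix A's event-specific rows govern where they differ from Table 0-8. For the residual row, the sponsor picks one Grade 2 rule and writes it identically in both places. If the looser rule is kept for tolerable Grade 2 fatigue, anorexia and weight loss, add these to Table 0-8's exceptions and to its continuation condition.
3. Add an infection row to Appendix A: hold temozolomide at Grade 2 or higher until Grade 1 or less, with no escalation during the hold; at Grade 3 or 4 follow the corrected Table 0-8; manage cabozantinib by section 4.4.3.14 for any infection.

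The cost is one table cell, one statement in two places, aligned wording for the residual row and one new row, all in a single amendment. No visits, tests or subjects are added and the Simon design is untouched. The downside is that some temozolomide doses will be missed for Grade 2 infection.

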APPENDIX B- DAILY DOSE CALCULATIONS BY BODY SURFACE AREA BSA

Total BSA (m²)	200 mg/m² (mg daily)	150 mg/m² (mg daily)
1.0	200	150
1.1	220	165
1.2	240	180
1.3	260	195
1.4	280	210
1.5	300	225
1.6	320	240
1.7	340	255
1.8	360	270
1.9	380	285
2.0	400	300
2.1	420	315
2.2	440	330
2.3	460	345
2.4	480	360
2.5	500	375

APPENDIX C – DRUG INTERACTION TABLES

Please refer to the drug interaction tables at the following websites for lists of substrates, inducers, and inhibitors of selected CYP450 isozyme pathways:

[Http://medicine.iupui.edu/clinpharm/ddis/table.aspx](http://medicine.iupui.edu/clinpharm/ddis/table.aspx)

**3.0 HTTPS://WWW.FDA.GOV/DRUGS/DRUG-
INTERACTIONS-LABELING/DRUG-
DEVELOPMENT-AND-DRUG-INTERACTIONS-
TABLE-SUBSTRATES-INHIBITORS-AND-
INDUCERS**

APPENDIX D – LABORATORY PANELS

Laboratory panels are composed of the following:

Hematology 
 WBC count with differential (including at minimum: neutrophils, basophils, eosinophils, lymphocytes, monocytes) hematocrit platelet count RBC count hemoglobin 		
Serum chemistry 
 albumin ALP amylase ALT AST bicarbonate BUN chloride creatinine GGT Glucose calcium lactate dehydrogenase lipase magnesium phosphorus potassium sodium total bilirubin total protein 		
Urinalysis 
 appearance color pH specific gravity ketones protein UPCR glucose bilirubin nitrite creatinine urobilinogen occult blood (microscopic examination of sediment will be performed only if the results of the urinalysis dipstick evaluation are positive) 		
Other 
 TSH (FT3, FT4) Pregnancy text (urine or serum) for women of child-bearing potential PT/INR or PTT 24 hour urine collection for protein 		

ALP, alkaline phosphatase; ALT, alanine aminotransferase; AST, aspartate aminotransferase; BUN, blood urea nitrogen; ESR, erythrocyte sedimentation rate ; GGT, γ -glutamyltransferase; INR, International Normalized Ratio; PT, prothrombin time; PTT, partial thromboplastin time; RBC, red blood cell; TSH, thyroid stimulating hormone; UPCR, urine protein/creatinine ratio; WBC, white blood cell.

APPENDIX E - ECOG PERFORMANCE STATUS

Grade	Description
0	Normal activity. Fully active, able to carry on all pre-disease performance without restriction.
1	Symptoms, but ambulatory. Restricted in physically strenuous activity, but ambulatory and able to carry out work of a light or sedentary nature (e.g., light housework, office work).
2	In bed <50% of the time. Ambulatory and capable of all self-care, but unable to carry out any work activities. Up and about more than 50% of waking hours.
3	In bed >50% of the time. Capable of only limited self-care, confined to bed or chair more than 50% of waking hours.
4	100% bedridden. Completely disabled. Cannot carry on any self-care. Totally confined to bed or chair.
5	Dead.
* As published in Am. J. Clin. Oncol.: Oken, M.M., Creech, R.H., Tormey, D.C., Horton, J., Davis, T.E., McFadden, E.T., Carbone, P.P.: Toxicity And Response Criteria Of The Eastern Cooperative Oncology Group. Am J Clin Oncol 5:649-655, 1982. The Eastern Cooperative Oncology Group, Robert Comis M.D., Group Chair.	

